10.3.3 Other events requiring reporting

10.3.3.1 Overdose

An overdose is defined as a subject receiving a dose of durvalumab (MEDI4736), tremelimumab, or azacitidine or oral decitabine (ASTX727) in excess of that specified in the Investigator's Brochure, unless otherwise specified in this protocol.

On a per dose basis, an overdose is defined as the following amount over the protocol-specified dose of durvalumab (MEDI4736), tremelimumab, or azacitidine or oral decitabine (ASTX727) assigned to a given patient, regardless of any associated adverse events or sequelae.

PO any amount over the protocol-specified dose

IV 10% over the protocol-specified dose

SC 10% over the protocol-specified dose

On a schedule or frequency basis, an overdose is defined as anything more frequent than the protocol required schedule or frequency.

On an infusion rate basis, an overdose is defined as any rate faster than the protocol-specified rate. Complete data about drug administration, including any overdose, regardless of whether the overdose was accidental or intentional, should be reported in the case report form.

Any overdose of a study subject with durvalumab (MEDI4736), tremelimumab, or azacitidine or oral decitabine (ASTX727), with or without associated AEs/SAEs, is required to be reported within 24 hours of knowledge of the event to the sponsor, AstraZeneca/MedImmune Patient Safety, or designee using the designated Safety e-mailbox (see Section 10.3.2 for contact information). If the overdose results in an AE, the AE must also be recorded as an AE (see Section 10.3). Overdose does not automatically make an AE serious, but if the consequences of the overdose are serious, for example death or hospitalization, the event is serious and must be recorded and reported as an SAE (see Section 10.3 and Section 10.3.2). There is currently no specific treatment in the event of an overdose of durvalumab (MEDI4736), tremelimumab, or azacitidine or oral decitabine (ASTX727).

The investigator will use clinical judgment to treat any overdose.

Date 09202024

10.3.3.2 Hepatic function abnormality

Hepatic function abnormality (as defined in Section 10.1.3.) in a study subject, with or without associated clinical manifestations, is required to be reported as "hepatic function abnormal" *within* 24 hours of knowledge of the event to the sponsor and AstraZeneca/MedImmune Patient Safety using the designated Safety e-mailbox (see Section 10.3.2 for contact information), unless a definitive underlying diagnosis for the abnormality (e.g., cholelithiasis or bile duct obstruction) that is unrelated to investigational product has been confirmed.

- If the definitive underlying diagnosis for the abnormality has been established and is unrelated to investigational product, the decision to continue dosing of the study subject will be based on the clinical judgment of the investigator.
- If no definitive underlying diagnosis for the abnormality is established, dosing of the study subject must be interrupted immediately. Follow-up investigations and inquiries must be initiated by the investigational site without delay.

Each reported event of hepatic function abnormality will be followed by the investigator and evaluated by the sponsor and AstraZeneca/MedImmune.

10.3.3.3 Pregnancy

All pregnancies or suspected pregnancies occurring in either a female subject or partner of a male subject are immediately reportable events.

10.3.3.3.1 Maternal exposure

Pregnancies and suspected pregnancies (including elevated β -hCG or positive pregnancy test in a female subject of reproductive potential, regardless of disease state) occurring while the subject is on IP, or within 90 days of the subject's last dose of IP, are considered immediately reportable events. The IPs should be discontinued immediately.

If any pregnancy occurs in the course of the study, then the Investigator or other site personnel should inform the appropriate AstraZeneca representatives within 1 day, ie, immediately, but **no later than 24 hours** of when he or she becomes aware of it using the Pregnancy Initial Report Form, or approved equivalent form. The female subject should be referred to an obstetrician-gynecologist, or another appropriate healthcare professional for further evaluation.

Pregnancy itself is not regarded as an AE unless there is a suspicion that the IP under study may have interfered with the effectiveness of a contraceptive medication. The Investigator will follow the female subject until completion of the pregnancy outcome and up to 1 year to monitor the baby,

Drug Substance Azacitidine/Decitabine (ASTX727)

Study Code 15-11430

Edition Number 13.0

Date 09202024

and must notify AstraZeneca Patient Safety within 1 to 5 calendar days for SAEs and within 30 days for all other pregnancies about the outcome of the pregnancy (either normal or abnormal outcome) using the Pregnancy Follow-up Report Form and Infant Follow-Up Form, or approved equivalent form.

Congenital abnormalities or birth defects, stillbirth, neonatal death, spontaneous or therapeutic abortion or miscarriage should be reported and handled as SAEs using the SAE Report Form, or approved equivalent form. In addition, any infant death after 28 days that the Investigator suspects is related to the in utero exposure to the IP should also be reported to Astrazeneca Patient Safety immediately by facsimile, or other appropriate method, within 24 hours of the Investigator's knowledge of the event using the SAE Report Form, or approved equivalent form. Elective abortions without complications should not be handled as AEs. The outcome of all pregnancies (spontaneous miscarriage, elective termination, ectopic pregnancy, normal birth, or congenital abnormality) should be followed up and documented even if the patient was discontinued from the study.

The designated AstraZeneca representative will work with the Investigator to ensure that all relevant information is provided to the AstraZeneca Patient Safety data entry site within 1 to 5 calendar days for SAEs and within 30 days for all other pregnancies.

10.3.3.3.2 Paternal exposure

Male patients should refrain from fathering a child or donating sperm during the study and for 180 days after the last dose of study drug.

Pregnancy of the patient's partner is not considered to be an AE. However, if a female partner of a male subject taking investigational product becomes pregnant, the male subject taking IP should notify the Investigator immediately, and the pregnant female partner should be advised to call their healthcare provider immediately. In addition, the outcome of all pregnancies (spontaneous miscarriage, elective termination, ectopic pregnancy, normal birth, or congenital abnormality) occurring from the date of the first dose until 90 days after the last dose should, if possible, be followed up and documented.

Where a report of pregnancy is received, prior to obtaining information about the pregnancy, the Investigator must obtain the consent of the patient's partner. Therefore, the local study team should adopt the generic ICF template in line with local procedures and submit it to the relevant Ethics Committees (ECs)/Institutional Review Boards (IRBs) prior to use.

Date 09202024

11 STATISTICAL METHODS AND SAMPLE SIZE DETERMINATION

Rational for Changes from SC Injection to Oral Drug

This trial opened with use of subcutaneous (SC) injection of azacitidine. Treatment, ie, 5 to 10 daily visits for a large-volume subcutaneous injection continuing for several months or even years, represents a significant hardship for patients. A possible consequence is non-compliance or earlier discontinuation of a beneficial treatment. Successful development of an oral DNA methyltransferase inhibitor will ease the burden of long-duration SC therapy, particularly for those patients who are benefitting the most and need continuing treatment for long periods.

The primary objective and design and number of doses to be tested with oral decitabine remain the same as in the original protocol which used SC injection of azacitidine. The overall sample size has been revised to account for accrual of patients who receive oral decitabine in addition to the patients accrued when the original protocol opened using SC injection of azacitidine.

The primary objective of the phase I trial is to determine the BED. The BED is to be determined among evaluable patients (eligible patients who at least begin protocol treatment and have an evaluable pre- and on-treatment (8-week) biopsy sample available). Three doses of oral decitabine (ASTX727) are scheduled to be tested. BED is defined as the dose of oral decitabine (ASTX727) that results in at least a 10% decrease in LINE-1 methylation from the baseline biopsy to the 8-week on-treatment tumor biopsy in at least 50% of patients treated within the same dose level. If the BED has not been determined in the first 2 dose levels and it is safe to do so, then the study will re-open to accrual and a subsequent group of 3 patients will receive the $3^{\rm rd}$ dose level. IF both the first 2 dose levels result in \geq 10% decrease in LINE-1 methylation, then the dose which induces the greatest fold change in HLA Class I/II APM expression and/or CD8+ T cell infiltration and with the lower adverse event profile will be the dose utilized for the dose expansion cohort. The change is a working rule and a panel of markers will be assessed and the dose with the most viable panel and lowest adverse event profile will be used in the expansion cohort.

Although assessment of the BED is primary, the dose also needs to be safe. Each dose will also be assessed for safety. Six patients will be entered into dose level 1. Adverse events (i.e. dose limiting toxicity (DLT) assessment as defined in section 6.4) will be assessed through 28 days post cycle 2. If two or more of the first six subjects experience a DLT, then the dose will be reduced and an additional six patients will be treated at the reduced dose. If two or more of the six at the reduced dose experience a DLT, then the study will be terminated. If at any time during accrual to a dose cohort, 2 or more patients in a dose cohort experience DLT, enrollment to that dose cohort will be terminated. If less than two of the six patients treated at dose level 1 experience a DLT, a subsequent group of six patients will receive dose level 2.

Drug Substance Azacitidine/Decitabine (ASTX727)

Study Code 15-11430

Edition Number 13.0

Date 09202024

Accrual will be suspended until review of the BED rate in tissue from baseline and 8 weeks post baseline has been completed from patients entered into the first 2 dose levels. If the BED has not been determined in the first 2 dose levels and it is safe to do so, then the study will re-open to accrual and a subsequent group of 6 patients will receive the 3rd dose level. Once the BED is determined, dose escalation will stop and the BED will be used in the expansion cohort.

Approximately 28 evaluable patients (eligible patients who at least begin protocol treatment and have an evaluable pre- and on-treatment (8-week) biopsy sample available) are estimated to be accrued during the BED assessment phase with the oral decitabine. This is based on studying 6 evaluable patients per dose level with a total of 3 dose levelsand an additional 10 evaluable patients entered at the BED ('expansion cohort' accrued to ensure that the BED rate is acceptable). The further assessment of the BED will be based on studying these 10 additional patients. Additional subjects may be enrolled into the cohort(s) to ensure that the required number of evaluable pre- and on-treatment biopsy samples are available to adequately determine the BED. See end of this statistical section for overall sample size.

BED is defined as outlined above. Six evaluable patients are estimated to be accrued per dose level with the additional 10 evaluable patients in the expansion cohort. The below table gives the probabilities of observing at least 33% of patients within a dose level with the BED for the first 6 patients for varying true rates of the BED.

True BED rate	Probability of ≥2 out of 6 patients in a dose level meet BED definition.	Probability of ≥7 out of 16 meet BED definition (given that ≥2 out of 6 patients in the dose level from original testing meet the BED definition plus the expansion cohort)
50%	.89	.73
55%	.93	.84
60%	.96	.92

For example, if the true rate of BED is 50%, the probability of observing ≥ 2 out of 6 patients in a dose level with the BED is 89%. The above table also shows the probabilities of successfully declaring the BED after cohort expansion (the additional 10 patients to a dose level) (last column). With 6 patients entered in a dose level and 10 in the expansion cohort (with cutpoints as in the above table), if the true BED rate were instead as low as 27%, the probability of a dose level being used as the BED in the phase II portion of this trial is only 10%.

With an estimated monthly accrual of 2 patients, accrual with use of the oral agent is estimated to complete in approximately 9 months. As of October 1, 2019, n=11 patients have been registered

Drug Substance Azacitidine/Decitabine (ASTX727)

Study Code 15-11430

Edition Number 13.0

Date 09202024

to receive SC injection of azacitidine. Accrual for patients to receive SC injection of azacitidine continues during review and approval of this amendment to change to administration of oral decitabine. With approximately 2-3 more patients enrolled to receive SC injection of azacitidine during amendment review, a total of up to N=41 (13 SC injection of azacitidine + up to 28 oral decitabine) patients could be entered.

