Drug Substance Azacitidine/Decitabine (ASTX727)

Study Code 15-11430

Edition Number 13.0

Date 09202024

decatibine (ASTX727) will be administered alone in Cycle 1 and the combination of oral decatibine (ASTX727) and durvalumab therapy will be administered in Cycles 2-12 or until confirmed PD, initiation of alternative cancer therapy, unacceptable toxicity, withdrawal of consent, or another discontinuation criterion is met, whichever occurs first. The BED will be assessed on pre-treatment and post-treatment biopsies obtained at week 8. BED is defined as the dose of oral decatibine (ASTX727) that results in at least a 10% decrease in LINE-1 methylation from the baseline biopsy sample to the 8-week on-treatment tumor biopsy sample in at least 50% of patients treated within the same dose level. Accrual will be suspended until review of the LINE-1 methylation level in tissue from baseline and 8 weeks post baseline has been completed from patients entered into the first 2 dose levels (oral decitabine on Days 1-3 alone and Days 1-4 in a 4-week cycle). If the BED has not been determined in the first 2 dose levels and it is safe to do so, then the study will re-open to accrual and a subsequent group of 3 patients will receive the 3^{rd} dose level. If both the first 2 dose levels result in > 10% decrease in LINE-1 methylation, then the dose which induces the greatest fold change in HLA Class I/II APM expression and/or CD8+ T cell infiltration and with the lowest AE profile will be the dose utilized for the dose expansion group. Once the BED is determined, dose escalation will stop and the BED will be used in the expansion cohort. Dose Limiting Toxicity (DLT) will be assessed through 28 days post Cycle 2.

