6.1.2 Procedures for randomization

This is not a randomized study. All eligible subjects will be allocated, by non-random assignment, to trial treatment and will receive a unique number. This unique number is termed a randomization number throughout the protocol for operational purposes. The randomization number identifies the subject for all procedures occurring after treatment allocation. Once a randomization number is assigned to a subject, it can never be re-assigned to another subject.

A single subject cannot be assigned more than one unique number. Treatment assignment will be done based on the schema described in **Sections 3.2 and 6.2, Table 2**. All patients will receive the same fixed dose of durvalumab (MEDI4736) and tremelimumab (based on a weight greater than 30 kg) and oral decitabine (ASTX727) will be dose escalated if safe to do so. Enrolled patients will be sequentially assigned to the cohorts. After the enrollment of 6 evaluable patients into the 1st group (eligible patients who at least begin protocol treatment and have an evaluable pre- and on-treatment (8-week) biopsy sample available), the next 6 patients will be enrolled into the 2nd cohort if safe to do so. After the enrollment of 6 evaluable patients into the 2nd cohort, the next 6 patients will be enrolled into the 3rd cohort only if the BED has not been determined, and the group in which the BED has been determined will be expanded to enroll 10 patients. Additional subjects may be enrolled into the cohort(s) to ensure that the required number of evaluable pre- and on-treatment biopsy samples are available to adequately determine the BED. Patients cannot change groups or dose assignments upon the initiation of the study protocol.

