6.2 Dosage and Administration

This is a phase Ib, open label dose escalation and safety evaluation of durvalumab (MEDI4736) and oral decitabine (ASTX727) combination therapy. This trial opened with the administration of subcutaneous (SC) injection of azacitidine. Treatment i.e. 5 to 10 daily visits for a largevolume SC injection continuing for several months or even years, represents a significant hardship for patients. A possible consequence is non-compliance or earlier discontinuation of a beneficial treatment. Successful development of an oral DNA methyltransferase inhibitor eases the burden of long duration SC therapy, particularly for those patients who are benefiting the most and need continuing treatment for long periods. In our trial with SC injection of azacitidine, we were achieving global tumor hypomethylation with clinical benefit. Furthermore, a tolerable AE profile was being observed. These preliminary results rationalize the continuation of this study but with an oral DNA methyltransferase inihibitor for reasons stated above. Since the oral DNA methyltransferase inhibitor is an investigational drug, we will administer the oral drug with the FDA approved durvalumab. We will continue treatment of azacitidine SC for those patients already enrolled into the study. However, all newly enrolled patients will receive an oral tablet of ASTX727 (35 mg decitabine/100 mg cedazuridine) daily on either Days 1-3, Days 1-4, or Days 1-5, and durvalumab (MEDI4736) 1500 mg via IV infusion x 1 in a 4 week cycle. Oral decatibine (ASTX727) will be administered alone in Cycle 1 and the combination of oral decatibine (ASTX727) and durvalumab therapy will be given in Cycles 2-12 or until confirmed PD, initiation of alternative cancer therapy, unacceptable toxicity, withdrawal of consent, or another discontinuation criterion is met, whichever occurs first. The BED will be assessed on pre-treatment and post-treatment biopsies obtained at week 8. BED is defined as the dose of oral decatibine (ASTX727) that results in at least a 10% decrease in LINE-1 methylation from the baseline biopsy sample to the 8-week on-treatment tumor biopsy sample in at least 50% of patients treated within the same dose level. Accrual will be suspended until assessment of the LINE-1 methylation levels in the first 2 dose cohorts. If the BED has not been determined in the first 2 dose levels and it is safe to do so, then the study will re-open to accrual and a subsequent group of 3 patients will receive the 3rd dose level. If both the first 2 dose levels result in > 10% decrease in LINE-1 methylation, then the dose which induces the greatest fold change in HLA Class I/II APM expression and/or CD8+ T cell infiltration and with the lowest AE profile will be the dose utilized for the dose expansion group. Dose Limiting Toxicity (DLT) will be assessed through 28 days post Cycle 2.

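### Dose level 3 is given both 3 and 6 patients, so Section 11 contradicts itself; its N of 28 and its probability table hold only for 6 per level plus 10 additional

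*Combined protocol and SAP*

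**What the plan says.** The oral part of the trial tests three schedules of ASTX727, with level 3 (Days 1-5) the highest. Level 3 opens only if the BED has not been found at levels 1 and 2 and it is safe to proceed. Its size is given as follows.

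| Place in the combined protocol and SAP | Patients at level 3 | Text |
|---|---|---|
| Section 3.1 | 3 | "a subsequent group of 3 patients will receive the" third dose level |
| Section 6.2 | 3 | "a subsequent group of 3 patients will receive the 3rd dose level" |
| Section 11, paragraph that defines the BED | 3 | "then the study will re-open to accrual and a subsequent group of 3 patients will receive the" third dose level |
| Section 11, paragraph on suspending accrual | 6 | "a subsequent group of 6 patients will receive the 3rd dose level" |
| Section 6.1.2 | 6 | "the next 6 patients will be enrolled into the 3rd cohort only if the BED has not been determined" |
| Section 3.2 schema, row B3 | 6 | cohort size shown in the row |
| Table 5a, row B3 | 6 | cohort size shown in the row |

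Section 11 bases its approximately 28 evaluable oral patients on 6 per level at three levels and "an additional 10 evaluable patients entered at the BED". Its table gives the probability of at least 2 of 6 and then at least 7 of 16 patients meeting the BED definition. The text under the table repeats the basis: "With 6 patients entered in a dose level and 10 in the expansion cohort". Section 6.1.2 instead says that the BED group "will be expanded to enroll 10 patients".

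Section 11 also forecasts oral accrual at 2 patients per month, finishing in about 9 months, and adds up to 28 oral patients to 13 azacitidine patients for a total of 41.

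**The concern.** The two Section 11 statements open with the same condition and end in different cohort sizes. Both are operative text, and Section 6.2 is where a site looks for dosing instructions. A site could treat either 3 or 6 patients at the highest level and point to the protocol for support.

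Three things depend on the answer: the DLT check, since enrolment to a cohort ends at two DLTs; the primary endpoint, since the only first-stage cutpoint is out of 6; and the total sample size. The accrual forecast drives no decision rule, but it does not fit the stated 28.

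**Working it through.** **1. Reproduce the plan's figures.** Inputs from Section 11: 6 per level, 3 levels, 10 additional at the BED, cutpoints 2/6 and 7/16, true BED rates 50%, 55%, 60% and 27%.

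- Sample size: 3×6 + 10 = 28, and 13 + 28 = 41. Both agree with the text.
- First stage: P(X ≥ 2), X ~ Bin(6, p). This gives .891, .931, .959, against .89, .93, .96 stated.
- Final column: the sum over x = 2 to 6 of P(X = x) × P(Y ≥ 7 − x), Y ~ Bin(10, p). This gives .735 (.7347 before rounding), .843, .917, against .73, .84, .92 stated. At p = .27 it gives .102, against 10% stated.

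The sample size and every table entry therefore rest on 6 per level plus 10 additional.

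**2. Put 3 at level 3.**

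- Total: 6 + 6 + 3 + 10 = 25.
- Cutpoints: the denominators become 3 and 3 + 10 = 13, so 2/6 and 7/16 cannot be applied. No cutpoint is given for 3. At a true rate of 50%, P(≥1 of 3) = .875 and P(≥2 of 3) = .50, so the choice matters. The 50% in the BED definition can be met only by 2 of 3 (67%).
- DLTs: P(≥2) = 3p²(1−p) + p³ for n = 3, and 1 − (1−p)⁶ − 6p(1−p)⁵ for n = 6. The true DLT rates below are illustrative.

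| True DLT rate | n = 3 | n = 6 |
|---|---|---|
| 20% | .096 + .008 = .104 | 1 − .262 − .393 = .345 |
| 30% | .189 + .027 = .216 | 1 − .118 − .303 = .580 |
| 40% | .288 + .064 = .352 | 1 − .047 − .187 = .767 |

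**3. Accrual.** Inputs from Section 11: 2 per month, about 9 months.

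- 9 × 2 = 18 patients, which equals the three cohorts of 6 without the expansion.
- 28 / 2 = 14 months.
- If levels 1 and 2 fill and level 3 is not opened: 6 + 6 + 10 = 22, and 22 / 2 = 11 months.
- To reach 28 in 9 months would need 28 / 9 = 3.1 per month.

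The 14 and 11 months are floors. They leave out patients without evaluable paired biopsies and all waiting time.

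**4. Expansion wording.** Read literally, Section 6.1.2 means 10 in total at the BED (6 + 4). Section 11 means 16 (6 + 10), and its 7/16 cutpoint needs 16.

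**The case against.** The best reply is that 6 is plainly meant: two tables, Section 6.1.2 and the whole calculation in Section 11 use it. A reader might go further and infer that the 3 is a slip to be overwritten. The documents do not establish that. The same sentence with 3 stands in three sections, so a deliberate change that was not carried through cannot be excluded. The calculation shows what was computed, which is strong but not conclusive evidence of intent.

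A reader might also infer that the sample size itself is wrong. It is not: 28 and the table are correct on their stated basis.

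The DLT contrast is fair only for the initial cohort. If level 3 became the BED, 10 more patients would be treated there, and it is unclear whether the two-DLT rule continues in the expansion. The percentages should not be read as the total chance of detecting toxicity at that dose.

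The accrual forecast is dated text, written as of October 2019 in a document now at version 13.0 of September 2024, and it is labelled approximate. That makes it secondary. One path does give 18 patients (6 + 2 + 10, if level 2 closes after DLTs in its first two patients), but Section 11 does not offer it as the basis for 9 months. It is tempting to add one 8-week biopsy wait and quote 14 + 1.8 = 15.8 months. That counts only one wait. The text also implies a DLT wait before level 2 and a level-3 biopsy wait before expansion, and three such waits give about 14 + 3×1.84 = 19.5 months. Since the actual pauses are not specified, only the floor is supportable.

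The expansion wording is largely settled by Section 11, which says several times that the 10 are additional. Sections 6.1.2 and 11 also already allow extra subjects to reach the evaluable number.

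**Conclusion.** The contradiction over level 3 stands: three statements give 3 and four give 6, with both numbers inside Section 11. At 6, everything in Section 11 except the accrual time reproduces. At 3, the total is 25, the stated cutpoints cannot be applied at that level, and the chance of seeing two or more DLTs in the initial cohort falls from 34% to 10%, 58% to 22%, and 77% to 35% at true rates of 20%, 30% and 40%. These probabilities assume independent patients with a common rate.

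The 9-month forecast is also wrong for 28 patients; at the stated rate it needs at least 14 months. This assumes that the 2 per month are all evaluable. The Section 6.1.2 expansion wording, and the use of the same 28 first for evaluable patients and then for patients entered, are minor.

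**What to change.** State one cohort size for dose level 3 and reconcile Sections 3.1, 3.2, 6.1.2, 6.2 with Table 5a, and both paragraphs of Section 11. Six is the size on which N = 28 and the table rest; if it is confirmed, the cost is wording only. If 3 is intended, restate N (25 on the present expansion) and supply cutpoints and probabilities for level 3.

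Secondary changes, all wording or restated figures:

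- Give oral accrual as at least 14 months for 28 evaluable patients, or at least 11 for 22 if both first levels fill and level 3 is not opened. Say that this is before the DLT and week-8 biopsy waits and any non-evaluable patients. If accrual is complete, give the actual figures.
- In Section 6.1.2, say that the 10 expansion patients are additional, 16 in total at that level.
- At the end of Section 11, label the 28 as evaluable, so that 41 is not read as a ceiling on patients entered.

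The 7/16 cutpoint should not be copied into Section 6.1.2 as it stands. The cutpoints are 2/6 = 33% and 7/16 = 44%, while the BED definition asks for at least 50%, and that difference needs its own reconciliation.
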